# **11.0 STATISTICAL CONSIDERATIONS**

# 11.1 Introduction

This is a Phase 2 randomized double-blind placebo-controlled trial to assess the impact of the live biotherapeutic product LACTIN-V containing *Lactobacillus crispatus* CTV-05 on the non-l*actobacillus* dominant microbiome of young women in South Africa at high risk of HIV acquisition.

The study plans to enrol and randomize 60 sexually experienced women age 18 to 23 years, who are using a reliable method of long- acting injectable birth control or are of nonchildbearing potential (permanently sterile). After enrolment, women will start a standard 7 day course of oral Metronidazole tablets. After completing the 7-day course of Metronidazole, subjects will be randomized to receive either placebo or LACTIN-V in a 1:2 ratio. The participants will receive protocol treatment for four weeks and will have four weeks of additional off treatment follow-up time.

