# 11.3 Sample Size Considerations

The study will accrue a total of 60 randomized subjects (n=20 for the placebo arm A and n=40 for the LACTIN-V arm B). The accrual for this study is expected to be completed within 75 weeks (18 months) with projected accrual rate of 3 subjects per month. Each subject will be followed up for 64 days.

The primary endpoint upon which the sample size calculation was based is the proportion of subjects with a  $\geq 1 \text{ Log}_{10}$  decrease in at least 3 of 9 proinflammatory cytokines in CVL specimens on the Day 36 Visit, i.e. at the completion of the LACTIN-V/Placebo dosing phase. The proportion of women with decreased inflammation will be compared between the two study arms. This endpoint is adapted from the CAPRISA 004 study which demonstrated that women with the highest levels of at least 3 of 9 proinflammatory cytokines in CVL specimens had an increased risk of HIV acquisition. Our adaptation of the CAPRISA 004 analysis is that we will define "decreased inflammation" as a  $\geq 1 \text{ Log}_{10}$ decrease in the concentration of at least 3 of the same 9 proinflammatory cytokines. Based on our prior data, we assume that no more than 10% of placebo-treated women will achieve a decrease in  $\geq 3$  of the 9 proinflammatory genital tract cytokines. Moreover, we hypothesize that at least half of the participants in the treatment arm will achieve a decrease  $\geq 1 \log_{10}$  in  $\geq 3$  of the 9 proinflammatory genital tract cytokines. With the targeted sample size of 60 randomized women (1/3 in placebo arm & 2/3 in the LACTIN-V arm; there will be more than 88% power to detect a 40% absolute difference (10% vs. 50%) in the proportion of women with decreased inflammation between the two treatment arms. This power calculation was based on simulation study using 10,000 Monte Carlo samples and two-sided Fisher's exact test with type 1 error rate of 5%.

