# 11.5. Statistical Analysis Plan

The primary analyses in Objective 1 is to compare the levels of i) pro-inflammatory genital tract cytokines levels & proportion of subjects with a significant decrease ( $\geq 1 \log_{10}$ ) in cytokines levels, ii) HIV target cells (i.e., CD4+/CCR5+/HLA-DR+/CD38+ T cells) and iii) anti-HIV effect of CVL, as assessed by HIV p24 levels, between the two treatment arms.

Graphical and descriptive measures (such as frequency, percent mean, median, standard deviation and IQR) will be used to summarize data. Spearman rank correlation will be used to examine associations among the aforementioned outcomes. Statistical tests (such as the two sample T and Wilcoxon rank sum tests) will be used to compare levels of cytokines, HIV p24 levels and HIV target cells between the two treatment groups.

For within group comparison, statistical tests (such as paired T and Wilcoxon signed rank tests) will be used. Longitudinal data analyses using nonlinear mixed models or generalized estimating equations will be performed to examine and compare the overtime changes in cytokines levels and HIV target cells. Fisher's exact test will be used to compare the proportion of subjects with a significant decrease ( $\geq 1 \log_{10}$ ) in cytokines levels.

Data classification and dimension reduction techniques (e.g., principal component analysis, and cluster analysis) will be used to group a set of cytokines or HIV target cells to uncorrelated summary variables or to identify study subjects with similar cytokine or HIV target cell profiles. Adjustment will be made for multiple comparisons using less conservative multiple testing correction procedures (such as the Holm's and Benjamini-Hochberg methods) where appropriate.

The primary analysis in Objective 2 is to compare the presence and abundance of *Lactobacillus spp*. (including *L. crispatus* CTV-05) between the two study groups. As in Objective 1, graphical and descriptive measures will be used to summarize data. Fisher's exact test will be used to compare presence of specific strains of vaginal lactobacilli and cervicotypes (CT). Empirical Bayes method will be used for identification of microbes that show differential abundance between study arms. Empirical Bayes method is more efficient due to its ability of pooling information across microbes.

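### Section 11.5 permits GEE with 20 and 40 women but fixes no scale, link or small-sample inference: run at the usual defaults its tests modestly exceed 5%, and the tests of levels leave the pre-dose value unused

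*Combined protocol and SAP*

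**What the plan says.** Section 11.3 fixes the arms at "n=20 for the placebo arm A and n=40 for the LACTIN-V arm B". It sizes the trial on a binary outcome: "The primary endpoint upon which the sample size calculation was based is the proportion of subjects with a" fall of at least 1 log10 in at least 3 of 9 cytokines at Day 36. In Section 11.5, "Fisher's exact test will be used to compare the proportion of subjects with a significant decrease".

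For the continuous outcomes, Section 11.5 gives two further layers:

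- Between-arm tests of levels, such as "two sample T and Wilcoxon rank sum tests) will be used to compare levels of cytokines", p24 and HIV target cells.
- For change over time in cytokines and target cells, "Longitudinal data analyses using nonlinear mixed models or generalized estimating equations will be performed to examine and compare the overtime changes".

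The longitudinal sentence names no outcome scale, link, working correlation, variance estimator, reference distribution, small-sample correction or covariate. Holm or Benjamini-Hochberg adjustment is promised where appropriate.

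Section 4.0 schedules cervicovaginal fluid and endocervical cells at Days 8, 36 and 64, so each woman has a value before her first dose. Section 11.2 takes the FRESH visit before enrolment as baseline. Section 3.4.1 names both that visit and Day 8.

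**The concern.** The usual GEE standard error is the robust (sandwich) one, referred to a normal or chi-square distribution. Both rely on many independent clusters. With 20 women in the smaller arm, the uncorrected sandwich variance is biased downward and the reference distribution is too narrow, so a true null is rejected more often than stated. Multiplicity adjustment works on the p-values and cannot repair a standard error that is too small.

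Target cells have no responder test of their own. Their planned between-arm evidence is the t or Wilcoxon comparison of levels plus this longitudinal model, which is the only stated between-arm method for change over time. With scale and link open, they could be chosen after the data are seen, and the permitted choices have quite different error rates.

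There is also a loss of efficiency. A two-sample comparison of levels discards a pre-dose measurement that the trial already collects.

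**Working it through.** **Inputs from the documents.** Arms of 20 and 40 (Section 11.3); three trial visits, Days 8, 36 and 64 (Section 4.0), or four if the FRESH visit is counted; two-sided 5%, stated for the Fisher test in Section 11.3. The documents give no SD or within-woman correlation, so those below are assumptions.

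**1. The plan's own figure.** Exact enumeration of all 21 × 41 tables for the two-sided Fisher test, 10% against 50%, gives power 89.1%. The stated power of more than 88% reproduces. The true size of that test is 2.8–3.6% for common response rates of 10–40%, so it is conservative.

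**2. Size of the bias by algebra.** With a saturated arm-by-visit mean, the uncorrected sandwich divides by n instead of n − 1 within each arm. For the between-arm difference in change:

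- variance ratio = [(19/20²) + (39/40²)] / [1/20 + 1/40] = (0.0475 + 0.024375) / 0.075 = 0.958
- standard-error ratio = √0.958 = 0.979, about 2% too small.

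The normal reference adds to this. A 400,000-run check of the single contrast gave a true size of 6.2%. The unbiased variance with a Satterthwaite t gave 5.0%.

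**3. Simulated size, identity link, uncorrected sandwich.** Null data, 20 against 40, within-woman correlation 0.5 assumed, 20,000 runs per scenario, nominal 5%:

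| Outcome | Visits | One arm-by-visit contrast | Joint test |
|---|---|---|---|
| Normal or t5 (as on log10 scale) | 3 | 6.0–6.1% | 7.1–7.3% |
| Normal or t5 | 4 | 6.0–6.2% | 8.0–8.3% |
| Raw log-normal | 3 or 4 | 5.1–5.4% | 5.7–6.4% |

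Other runs of the normal case reached about 6.5% for the single contrast and 7.6% for the joint test. An assumed 15% loss (17 against 34) gave 5.3–6.7% and 5.9–9.3% across all these shapes and visit numbers. A Mancl-DeRouen standard error with a t or F reference brought the normal three-visit case back to 4.7% and 5.1%. GEE with a model-based standard error and the correct exchangeable correlation gave 5.0%.

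**4. Simulated size, raw counts on a log link.** Assumed median 50, within-woman correlation 0.4, three visits, 20,000 runs, uncorrected sandwich. Ranges are across independent runs:

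| Between-woman SD (natural log) | Change to Day 36 | Joint Days 36 and 64 | Same counts, identity link |
|---|---|---|---|
| 1.0 | 9.2–9.3% | 12.2–12.4% | 5.4% |
| 1.5 | 13.9–14.6% | 19.9–20.8% | 4.2% |
| 2.0 | 21.3–21.4% | 31.3–31.4% | 3.2% |

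The inflation here comes from pairing a log link with skewed counts. Bias-corrected standard errors with a t reference still left 7–19%.

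**5. What the pre-dose value buys.** Assume an effect of 0.5 log10 and an SD of 1.5 on the natural-log scale, which is 1.5 / 2.303 = 0.651 log10.

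- Standard error of the difference in levels: 0.651 × √(1/20 + 1/40) = 0.178.
- Signal to noise: 0.5 / 0.178 = 2.80. Approximate power: Φ(2.80 − 1.96) = 0.80.
- Adjusting for a baseline with correlation ρ multiplies the residual variance by 1 − ρ²: 0.91, 0.75 and 0.64 at ρ = 0.3, 0.5 and 0.6. Approximate power becomes 0.84, 0.90 and 0.94.

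Simulation on log10(count + 1), which includes count noise, gave 0.75–0.78 for the two-sample t test and 0.80, 0.86–0.87 and 0.90–0.91 with adjustment. The size of the adjusted test was 4.8–5.4%.

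**The case against.** The strongest reply is that the plan commits to none of this. Mixed models are named first, GEE is an alternative, and robust standard errors are a software default that the text never mentions. With a model-based standard error and the right working correlation, GEE held 5.0%. This stands: the point is conditional on GEE being run at its usual settings.

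Second, the outcomes have other tests. The responder endpoint uses Fisher's exact test, and levels are compared by t and Wilcoxon tests. In null runs the Day 36 t test on log10(count + 1) held 4.8–5.3%. This also stands, and it makes the longitudinal model a supporting analysis.

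Third, a longitudinal model of change already uses the baseline visit as an outcome, so the covariate concerns power and not error rate. That is right. The baseline gain is a separate benefit, measured against the two-sample tests of levels.

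A reader might infer that GEE as planned will produce false target-cell findings at 9–31%. The documents do not support that. Section 11.5 names no link and does not say that raw counts will be modelled, and the medians, SDs and correlation behind those rates are assumed. The background section reports a 17-fold difference in target-cell numbers between cervicotypes, which makes wide spread plausible but does not give an SD.

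**Conclusion.** The concern holds as a specification gap in a supporting analysis, of minor to moderate weight. If GEE is run with an uncorrected robust standard error and a normal or chi-square reference, a nominal 5% test on the log10 scale is really about 6–6.5% for a single arm-by-visit contrast and 7–8% for the joint test. These figures rest on full follow-up and roughly normal or t5 log10 values, with the correlation assumed. The larger rates belong to one unstated modelling choice and should not set the severity. They are a reason to state the scale and link in advance.

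A reader might also take this as a threat to the trial's main result. It is not: the powered Day 36 comparison is untouched, and its power statement is correct.

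The more useful gain is efficiency. Adjusting for a value that is already collected adds roughly 3 to 16 percentage points of power over the two-sample t test across the assumed correlations of 0.3 to 0.6 (from 0.77–0.78 to 0.80 and from 0.75–0.77 to as much as 0.91).

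**What to change.** In Section 11.5, replace the choice between nonlinear mixed models and GEE with one stated model:

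- Outcome: log10 concentration for cytokines and log10(count + 1) for target cells, at Days 36 and 64.
- Linear mixed model with arm, visit, arm-by-visit and the woman's pre-randomization log10 value as covariate, fitted by REML with Kenward-Roger degrees of freedom.
- State which baseline is the covariate, the FRESH visit or Day 8, and reconcile Sections 3.4.1 and 11.2 accordingly. Both precede randomization, so either is a valid covariate.

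If GEE is kept, specify the log10 scale with identity link, a Kauermann-Carroll or Mancl-DeRouen standard error, and a t or F reference. Do not fit raw target-cell counts on a log link, because the correction does not rescue that case.

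The cost is SAP wording only, with no new samples or visits. Intervals will be slightly wider than from uncorrected GEE.

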#### 5.3 Treatment Assignment Procedures

#### 5.3.1 Randomization Procedures

Women will be randomized at the Randomization Visit 3 (Day 8) upon completion of the initial standardized antibiotic treatment with 2 x 400 mg daily over 7 days of oral metronidazole.

Women will be randomly assigned to receive LACTIN-V at  $2 \times 10^9$  cfu/dose or placebo in a 2:1 ratio. Enrolment will be continued until 60 women are randomized.

The list of randomized treatment assignments will be prepared by a statistician not involved with the study, and provided to the pharmacy, who will label the applicator pouches and cartons. Each carton will contain 11 study treatment applicators and be sequentially numbered according to the randomization scheme in a 2:1 (LACTIN-V to placebo) ratio.

Disenrolled participants before randomization will be replaced until 60 women are randomized into the study. Once randomized, participants will not be disenrolled.

Participants who test HIV-positive after randomization, will discontinue study product, but continue follow-up and attend all remaining study visits to monitor for adverse events. HIV-specific care, including the provision of antiretroviral treatment and ongoing management will be provided by the FRESH Study.

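### Fisher's exact test is valid for the primary comparison, but at 20 versus 40 women its true type I error is at most 3.7%; Boschloo's test, with its version fixed in advance, gives somewhat more power within 5%

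*Combined protocol and SAP*

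**What the plan says.** Section 11.3 sizes the trial on the proportion of women whose concentrations fall by at least 1 log10 in at least 3 of 9 cytokines at Day 36. The arms are "n=20 for the placebo arm A and n=40 for the LACTIN-V arm B", in line with the 2:1 allocation in section 5.3.1. For placebo, "we assume that no more than 10% of placebo-treated women will achieve a decrease in" at least 3 of the 9 cytokines. For LACTIN-V, "we hypothesize that at least half of the participants in the treatment arm will achieve a decrease" of that kind. On these inputs "there will be more than 88% power", obtained from 10,000 Monte Carlo samples and a "two-sided Fisher's exact test with type 1 error rate of 5" per cent.

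Section 11.5 carries the test into the analysis: "Fisher's exact test will be used to compare the proportion of subjects with a significant decrease" of at least 1 log10 in cytokine levels. That sentence does not repeat the 3-of-9 rule; the link to the primary endpoint comes from 11.3, which names the same test.

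Neither section reports the actual size of Fisher's test at these numbers, considers an unconditional exact test, or allows for missing Day 36 samples in the power figure. Section 5.3.1 replaces only women lost before randomization.

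**The concern.** Fisher's test conditions on the total number of responders. With 20 and 40 women that conditional distribution is coarse, so the test cannot use its full nominal 5% and gives up power that an unconditional exact test can use while still holding 5%.

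What is at stake is modest but concrete. If 18 and 36 women are evaluable and the result is 2/18 (11%) versus 14/36 (39%), Fisher gives p = 0.0565 and the primary comparison is reported as not significant. Boschloo's test rejects on the same table, because its cut-off on the Fisher p-value at that size is 0.0692. In a 60-woman Phase 2 trial, the choice of test would then decide how a 28-point difference is described.

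**Working it through.** **Inputs.** From section 11.3: n = 20 placebo and 40 LACTIN-V, response rates 10% and 50%, two-sided Fisher's exact test at 5%, stated power more than 88%. Missing-sample rates are an assumption (5% to 20%), because the documents give none.

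**Step 1: the plan's own figure.** Let a and b be the responders in each arm and p_F(a,b) the two-sided Fisher p-value.

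Power = sum over all (a,b) of Bin(a; 20, 0.10) × Bin(b; 40, 0.50) × 1[p_F(a,b) ≤ 0.05]

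Summing over all 21 × 41 tables gives **89.1%**, and a 10,000-sample simulation gives the same. The stated figure reproduces.

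**Step 2: Fisher's actual size.** With a common response rate π in both arms,

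Size(π) = sum over all (a,b) of Bin(a; 20, π) × Bin(b; 40, π) × 1[p_F(a,b) ≤ 0.05]

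Over a grid of 9,999 values of π from 0.0001 to 0.9999 the maximum is **3.69%**. At π = 10% it is 2.8%.

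**Step 3: Boschloo's test on the two-sided Fisher p-value.** Replace 0.05 in the indicator by the largest cut-off c for which the maximum of Size(π) is still at most 5%. Because Fisher's region at 0.05 already satisfies that bound, c cannot be below 0.05, so this version rejects every table that Fisher rejects. At 20/40, c = 0.0575, the maximum size is **4.88%** and the power is **90.6%**, a gain of 90.6 − 89.1 = 1.5 points.

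**Step 4: missing samples left out of the comparison (assumed).** Power for 10% versus 50%:

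| Evaluable (placebo/LACTIN-V) | Missing of 60 | Fisher | Boschloo | Gain (points) |
|---|---|---|---|---|
| 20/40 | 0 | 89.1% | 90.6% | 1.5 |
| 19/38 | 3 (5%) | 87.7% | 89.6% | 1.9 |
| 18/38 | 4 (6.7%) | 86.2% | 87.2% | 1.0 |
| 17/39 | 4 (6.7%) | 85.2% | 86.5% | 1.3 |
| 18/36 | 6 (10%) | 84.9% | 89.2% | 4.3 |
| 17/34 | 9 (15%) | 81.2% | 87.0% | 5.8 |
| 16/32 | 12 (20%) | 77.1% | 84.9% | 7.8 |

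Boschloo's maximum size stays below 5% in every row. The gain is not smooth in the number lost, because both tests are discrete. At 18/38 Boschloo recovers (87.2 − 86.2)/(89.1 − 86.2) = 1.0/2.9, about a third of the loss; at 18/36 it recovers all of it. Averaged over random splits, power goes from 86.1% to 87.6% with 4 missing and from 84.8% to 88.7% with 6 missing.

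**Step 5: missing counted as non-response (assumed).** With 10% missing the rates become 0.10 × 0.9 = 0.09 and 0.50 × 0.9 = 0.45 on 20 and 40 women. Power is 83.3% for Fisher and 84.3% for Boschloo, a gain of 1.0 point. At 5% missing it is 86.4% against 87.7%; at 15%, 79.7% against 80.5%.

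**Step 6: the version matters.** A common software default for Boschloo's test doubles the smaller one-sided p-value instead. For 16/20 placebo versus 36/37 LACTIN-V responders, Fisher gives p = 0.047 and that default gives 0.057, so it does not always reject when Fisher does. Its power for 10% versus 50% also differs: 91.3% at 20/40, 88.2% at 18/36 and 85.5% at 17/34.

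**The case against.** The strongest reply is that nothing in the plan is wrong. Fisher's test is named in advance, used for both design and analysis, and controls type I error; its conservatism is already inside the stated power. At full data the alternative adds 1.5 points, and choosing between a conditional and an unconditional exact test is partly a matter of taste. All of that stands, and it is why this is a suggestion only.

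A reader might infer that Boschloo's test restores most of the power lost to a few missing samples, or keeps power above 88% for anything up to 10% missing. The figures do not support either as a general statement. With 4 missing, fewer than the 6 in the 10% case, average power under Boschloo is 87.6%, and at 18/38 only about a third of the loss comes back. If missing counts as non-response, little comes back.

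It is also fair to say that missing samples are a separate matter. The documents give no rate, and the design works to limit losses: twice-weekly visits shared with FRESH, a Day 33 to 43 window for the Day 36 visit, and continued follow-up after product is stopped. Sections 5.3.3 and 5.3.4 still foresee withdrawal of consent and loss to follow-up after randomization, so some loss is plausible, but its size is unknown.

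Finally, Boschloo's test is not one test. The dominance over Fisher holds for the version ordered by the two-sided Fisher p-value and fails for the doubled one-sided version. That objection is met only by naming the version.

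**Conclusion.** The point holds as a cheap efficiency improvement. At 20/40 Fisher's maximum size is 3.7%. Boschloo's test on the two-sided Fisher p-value has maximum size 4.9%, loses no rejection, and raises power for 10% versus 50% from 89.1% to 90.6%. With assumed losses of 5% to 20% left out of the comparison, the gain is between 1.0 and 7.8 points in the cases tabulated and depends on the split between arms.

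A reader might take this to mean that Fisher's test is invalid or that the power in 11.3 is overstated. Neither follows: the test holds its level and the figure is correct with 60 evaluable women. The 3.7% also belongs to the planned size; at some reduced sizes Fisher's maximum is slightly above 4% (4.24% at 18/36), still below 5%. The results rest on the plan's 10% and 50% rates. No case is made here for changing the Objective 2 tests, for which the documents give no power figure.

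**What to change.** Before unblinding, amend sections 11.3 and 11.5 to say that the Day 36 primary proportion (at least 1 log10 decrease in at least 3 of 9 cytokines) is compared by Boschloo's unconditional exact test at two-sided 5%. State that the ordering statistic is the two-sided Fisher p-value, that the p-value is its null tail probability maximised over the common response rate at the evaluable numbers per arm, and that the version doubling the smaller one-sided p-value is not used. Keep Fisher's p-value as a supporting figure.

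State in the same place whether a missing Day 36 sample is left out or counted as non-response, since the gain depends on it. An allowance for missing samples in 11.3 is still needed separately.

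The cost is a less familiar test name, a few sentences of text, and a few lines of code, because a software default may compute the other version. No extra women, visits or samples are needed.

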#### 3.3 Study Objectives

#### 3.3.1 Primary Objectives

- 1) Determine the effect of repeat dosing of LACTIN-V (2 x 10^9 cfu/dose) on genital tract inflammation in young South African women at risk of HIV.
- 2) Determine the ability of LACTIN-V to promote a *Lactobacillus*-dominant vaginal microbiota in young South African women at risk of HIV.
- Determine the safety and acceptability of LACTIN-V in a population of young South African women at risk for HIV.

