#### 3.4 Study Outcome Measures

#### 3.4.1 Primary/ Secondary Outcome Measures

# *Primary / Secondary Outcome Measures for Objective 1 (effect on genital tract proinflammatory cytokines and HIV target cells)*

The proportion of participants with decreased genital tract proinflammatory cytokines and HIV target cells at 6 and 10 weeks of follow up, compared to levels at the baseline FRESH Study Visit, and Randomization Visit on Day 8 of the study (after treatment with Metronidazole is completed).

Our outcome will be a change after 4 weeks of treatment with LACTIN-V in comparison to

placebo, for the following:

- i. a decrease of the concentrations of proinflammatory cytokines in genital fluid that have been associated with risk for HIV acquisition,
- ii. a decrease in the number of activated HIV target cells (i.e. CD4+/CCR5+/HLA-DR+/CD38+ T cells) in the endocervix and
- iii. an increase the anti-HIV effect of vaginal secretions relative to placebo.

*Primary / Secondary Efficacy Outcome Measures for Objective 2 (promoting Lactobacillusdominant microbiota)* 

1:

The proportion of participants with increased *Lactobacillus*-dominant vaginal microbiota in young South African women, compared to levels at randomization (Day 8) after completion of metronidazole. Measured will be overall *Lactobacillus* species, as well as *Lactobacillus crispatus*, *Lactobacillus jensenii*, *Lactobacillus gasseri*, and *Lactobacillus iners*.

Our primary outcome is the presence of *Lactobacillus*-dominant vaginal microbial cervicotypes after 4 weeks of treatment with LACTIN-V, and following the post- dosing phase at Day 64.

Secondary outcomes include comparison of *L. crispatus* vs. *L. iners* prevalence between treatment groups, persistence of colonization after stopping therapy, effect of sex and/or vaginal hygiene practices on colonization by lactobacilli, and stability of vaginal microbial communities over time in the treatment vs. placebo group.

2:

The proportion of participants with a positive BV diagnosis in each study arm by Day 64.

BV is defined Nugent score 7-10. Following FDA guidance all BV diagnoses during follow-up visits are considered incident, as they occur at least 22-30 days after the commencement of Metronidazole treatment and consequently are treatment failures or new infections. For the purpose of this trial, treatment failure and new infection will both be considered recurrent BV.

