#### 3:

The proportion of participants experiencing successful colonization with *L. crispatus* CTV-05 following dose of study product through final visit (approximately Day 36 and 64) in the LACTIN-V arm.

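### The primary Objective 2 analysis in section 11.5 does not match the stated primary outcome of Lactobacillus dominance, and one of its components, presence of the product strain, cannot support the Objective 2 conclusion

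*Combined protocol and SAP*

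**What the plan says.** Section 3.3.1 gives Objective 2 as: "Determine the ability of LACTIN-V to promote a *Lactobacillus*-dominant vaginal microbiota in young South African women at risk of HIV". Section 3.4.1 turns this into an endpoint: "Our primary outcome is the presence of *Lactobacillus*-dominant vaginal microbial cervicotypes after 4 weeks of treatment with LACTIN-V", and again at Day 64. The same section lists CTV-05 separately as item 3, beginning "The proportion of participants experiencing successful colonization with" the strain and confined to the LACTIN-V arm at about Days 36 and 64. Item 4 compares cervicotypes I-IV by arm.

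Section 11.2 keeps the same order. Dominant cervicotypes at Days 36 and 64 are in item (1), although worded there for the LACTIN-V arm. Presence of the CTV-05 strain is in item (2), among the further outcomes.

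Section 11.5 departs from this. Its primary Objective 2 analysis is to "compare the presence and abundance of *Lactobacillus spp*. (including *L. crispatus* CTV-05) between the two study groups". Fisher's exact test is then assigned both to the presence of particular strains and to cervicotypes, without ranking them. A Benjamini-Hochberg type of adjustment is planned, but the family of tests is not defined. The Objective 2 text of section 11.5 does not mention dominance and fixes no visit.

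**The concern.** The analysis section should say which comparison answers the objective. Here it describes a broader set than the endpoint section does, and the set includes a test whose result is largely settled by the design. CTV-05 is the organism in the product, and section 6.1 describes the placebo as the matching formulation without it. A between-arm test of CTV-05 presence therefore asks mainly whether women given the strain can be shown to carry it. It uses no information on whether lactobacilli dominate the community.

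The problem is sharper at the end of dosing. The last dose is on Day 32 and the Day 36 visit window opens on Day 33 (section 7.5), so a sample may be taken one day after product was inserted. The documents set no threshold that separates residual product from colonisation.

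At stake is the reading of a result. With no deciding comparison named, a significant CTV-05 difference could be presented as a positive primary Objective 2 finding while the proportion with a dominant cervicotype is the same in both arms.

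**Working it through.** **Inputs from the documents.** Arm sizes are "n=20 for the placebo arm A and n=40 for the LACTIN-V arm B" (section 11.3). The test is Fisher's exact, two-sided, 5%; section 11.3 states sidedness and level for the cytokine endpoint, and they are carried over here. CTV-05 colonisation rates are in section 2.4: 42% (earlier capsule trial, intention to treat), and in LV-006 61% of 18 women overall and 78% of complete adherers.

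**Assumptions.** CTV-05 detection on placebo is 0-5%, with 10% as a stress case. Placebo dominance is 10-50%. The documents give neither. All 60 women are taken as evaluable.

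**Step 1: the plan's own power figure.** Summing binomial probabilities over every table that Fisher rejects, for 10% of 20 against 50% of 40, gives 89.1%. Section 11.3 states more than 88%, so its figure is reproduced. The same enumeration is used below.

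**Step 2: smallest significant CTV-05 split with 0/20 on placebo.** With k positives, all on LACTIN-V, the table probability is C(40,k)/C(60,k). The two-sided p-value adds every table that is no more probable.
- k = 7: 0.0483 + (0.0313 + 0.0040 + 0.0002) = 0.084.
- k = 8: 0.0301 + (0.0118 + 0.0012 + 0.00005) = 0.043.

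So 8/40 (20%) is enough.

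**Step 3: probability that the CTV-05 test is significant.** With no placebo detections this is P(X >= 8), X ~ Binomial(40, p). Otherwise it is the full enumeration.

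| True detection on LACTIN-V | Placebo 0% | Placebo 5% | Placebo 10% |
|---|---|---|---|
| 20% | 0.56 | 0.26 | 0.12 |
| 25% | 0.82 | 0.46 | 0.23 |
| 30% | 0.94 | 0.64 | 0.37 |
| 42% | 0.999 | 0.91 | 0.73 |
| 61% | >0.999 | 0.998 | 0.98 |

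At 10% detection and no placebo detections it is 0.04.

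**Step 4: stricter levels, as a stand-in for multiplicity adjustment** (placebo 0%). At 0.005: 0.92 at 42% and 0.9999 at 61%. At 0.001: 0.66 and 0.998.

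**Step 5: the dominance test on the same women.** For placebo dominance of 10-50%, Fisher on the proportion with a dominant cervicotype rejects with these probabilities:
- no difference: 0.028-0.036
- 20-point gain: 0.23-0.37
- 30-point gain: 0.51-0.67
- 40-point gain: 0.80-0.90

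The dominance test follows the objective. The CTV-05 test can be significant when dominance is unchanged.

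**The case against.** A reader might infer that the whole primary Objective 2 analysis is a CTV-05 test and is bound to succeed. The documents do not support that. CTV-05 is one named member of a genus-wide comparison of presence and abundance, cervicotypes are also tested, and multiplicity adjustment is planned. Nothing in the text says that one significant p-value decides the objective. Section 4.0 calls Objective 2 a secondary outcome, and the sample size rests on the cytokine endpoint.

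Nor does section 11.5 strictly contradict item 3 of section 3.4.1. A within-arm proportion and a between-arm comparison can stand together, and section 11.2 lists CTV-05 presence among outcomes that include treatment-versus-placebo comparisons.

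The cited rates are also imperfect guides. The 42% comes from a lower-dose capsule. The 61% counts colonisation at Day 10 and/or Day 28 in 18 women after topical metronidazole. Neither is a single-visit rate in this population. In LV-006, colonised women also had lower levels of BV-associated bacteria, so high colonisation with no change in dominance is a hypothetical case.

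Finally, section 4.0 describes Objective 2 in terms of durable colonisation by CTV-05. At Day 64, 32 days after the last dose, detection is informative about persistence.

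All of this stands. It limits the point to one component and makes its near-certainty conditional on the detection rate. It does not remove the mismatch between section 11.5 and the primary outcome. It also does not make strain presence a measure of dominance. Multiplicity adjustment changes the threshold, not what the test measures.

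**Conclusion.** The point holds as a mismatch between analysis and endpoint. Section 11.5 states a primary Objective 2 analysis that is wider than the dominance outcome in section 3.4.1 and item (1) of section 11.2, and it names no deciding comparison or visit. The CTV-05 component cannot carry the Objective 2 conclusion, because at the colonisation rates the protocol cites it would very probably be significant with or without a change in dominance.

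The size of this depends on two quantities the documents do not give: placebo detection, and single-visit detection on LACTIN-V. Near-certainty needs roughly 30% detection or more when no placebo woman is positive, and more than that if placebo detections occur. Evaluability matters less: with 17 and 34 evaluable women and no placebo detections, the probability is still 0.84 at 30% and 0.99 at 42%. The defect affects how a result is claimed. It should be corrected, but it does not undermine the trial.

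**What to change.** In section 11.5:

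1. Name as the primary Objective 2 analysis the between-arm Fisher comparison of the proportion with a Lactobacillus-dominant cervicotype at Day 36, with Day 64 as the persistence comparison. Align item (1) of section 11.2, which is worded for the LACTIN-V arm.
2. Move presence and abundance of individual Lactobacillus species and strains to secondary analyses. Deleting the parenthesis on CTV-05 would not be enough: the strain would still be counted within L. crispatus and Lactobacillus spp., and the test of specific strains would remain.
3. Report CTV-05 colonisation as item 3 of section 3.4.1 does: the number colonised out of the LACTIN-V arm at Day 36 and at Day 64, with an exact 95% interval (for illustration, 24/40 = 60%, interval 43% to 75%). Show placebo detections as a contamination or assay check.

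One limit remains. CTV-05 also contributes to the cervicotype, so dominance at Day 36 is not wholly free of recently inserted product. The Day 64 comparison helps with this.

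No sample, assay or visit is added. The cost is wording changes and the loss of a near-certain significant p-value from the primary analysis. What replaces it is a test with 80-90% power only for a gain of about 40 points.
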